The participant population in both Part 1 and Part 2 will include at least 40% of participants with moderate AD (IGA score of 3) and at least 40% of participants with severe AD (IGA score of 4). The application of topical emollients/moisturizers (including those containing ceramide, hyaluronic acid, or urea) will be required at least once daily for at least 1 week prior to baseline (Day 1) and throughout the treatment period without change (ie, type, frequency, application). TCS and other medicated topical treatments for AD must be discontinued at least 1 week prior to baseline (Day 1) and are not permitted in the double-blind treatment period. Safety follow-up visits will occur at 2 and 4 weeks after the last dose of study treatment. Medicated and non-medicated rescue medications are not permitted during the Part 1 DB portion. For Part 1 OLE and Part 2 medicated and non-medicated topical treatments for AD will be permitted at the discretion of the investigator and in accordance with their usual practice.

Number of Participants:

Part 1: Approximately 60 participants will be randomized in the DB period. Participants who qualify based on acceptable safety and who complete the DB period will continue in the OLE.

Part 2: Approximately 340 participants will be enrolled in this OL part of the study.

Study Population:

Key inclusion and exclusion criteria are listed below:

Inclusion Criteria

Participants must meet the following key inclusion criteria to be eligible for enrollment into the study:

- 1. Chronic AD (also known as atopic eczema) that was diagnosed at least 1 year prior to Screening and meets Hanifin and Rajka criteria at screening).¹
- 2. Moderate-to-severe AD:
 - a. IGA score ≥ 3 (on the 0 to 4 IGA scale, in which 3 = moderate and 4 = severe) at screening and baseline (Day 1)
 - b. BSA $\geq 10\%$ of AD involvement at screening and baseline (Day 1)
 - c. Eczema Area and Severity Index (EASI) ≥16 at screening and baseline (Day 1)
- 3. A participant who has failed a prior systemic therapy for AD, ie, refractory, moderate-to-severe AD that is not adequately controlled with other systemic drug products, including biologics, or when use of those therapies is inadvisable (i.e., medical contraindications to systemic therapy prohibit use).

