1.3.1. Part 1 (DB and OLE) Screening and Treatment Period

Visit Identifier	Screen	DB Treatment Period						OLE	Treat	ment F	Period		Notes
Abbreviations used in this table may be found in													
Appendix 12													
		Day 1	Week 4	Week 8	Week 12	Week 16	Wee k 20		Week 32	Week 40	Week 52	Week 68	 Screening, and all visits during the 16 Week DB Treatment Period including Safety Follow up Visits MUST be conducted at the investigative study site. Home health and/or telehealth visits may apply for certain extenuating circumstances only during the OLE Treatment period. See Section 8.1.2 and Section 8.1.3 Due to first dose cardiac monitoring Day 1 and Week 16 visits should be conducted in the morning and not on a Friday or the day before a site-observed holiday. See Section 10.10.3. In preparation for the Week 16 visit, site is to contact participant 1-2 business days prior to visit to remind them they will take study intervention at the site. See Section 6.5.
Study Day	-28 to -	1	29	57	85	113	141	169	225	281	365	477	• Day relative to start of study intervention (Day 1).
Visit Window (±days)	NA	NA	(±5)	(±5)	(±5)	(±5)	(±5)	(±7)	(±7)	(±7)	(±7)	(±7)	 All screening should be done ≤ 28 days before the first dose. See Section 8.4.3 for follow-up AE and SAE assessments.
Informed consent	X												 Informed consent should be obtained prior to undergoing any study-specific procedures. See Section 10.1.3 for additional information.

Visit Identifier Abbreviations used in this table may be found in Appendix 12	Screen]	DB Tre	eatmen	t Perio	d		OLE Treatment Period					Notes			
		Day 1	Week								Week		• Screening, and all visits during the 16 Week DB			
			4	8	12	16	k 20	24	32	40	52	68	 Treatment Period including Safety Follow up Visits MUST be conducted at the investigative study site. Home health and/or telehealth visits may apply for certain extenuating circumstances only during the OLE Treatment period. See Section 8.1.2 and Section 8.1.3 Due to first dose cardiac monitoring Day 1 and Week 16 visits should be conducted in the morning and not on a Friday or the day before a site-observed holiday. See Section 10.10.3. In preparation for the Week 16 visit, site is to contact participant 1-2 business days prior to visit to remind them they will take study intervention at the site. See Section 6.5. 			
Study Day	-28 to -	1	29	57	85	113	141	169	225	281	365	477	• Day relative to start of study intervention (Day 1).			

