6.9.3. Prohibited During the Study

In the event of an emergency, any needed medications may be prescribed without prior approval, but the study medical monitor must be notified of the use of any prohibited medications immediately.

Prohibited Medications Not Requiring Interruption or Discontinuation of Study Treatment

- The following therapies are prohibited during the study until completion of study treatment. Participants receiving any of the following must discontinue such use immediately without interruption or discontinuation of study treatment:
- Low-to-moderate potency TCS (Class VII-IV), calcineurin inhibitors (eg, tacrolimus and pimecrolimus), or crisaborole or high potency TCS (Class III-I) administered for <7 consecutive days. TCS classes (VII-IV) are based on WHO classification of topical corticosteroids^{34,35}). See CRF guidelines.
- Topical antihistamines, tars, topical anesthetics, or antibiotic creams

- Sedating, systemic antihistamines (eg, diphenhydramine, hydroxyzine, promethazine) (nonsedating systemic antihistamines are allowed)
- Initiation of any new (ie, during the screening and treatment period) emollients/moisturizers containing additives such as ceramide, hyaluronic acid, urea, antipruritic or antiseptic agents during the screening and treatment period (patients may continue using stable doses of such emollients/moisturizers if initiated before the screening visit)

Prohibited Medications Requiring Permanent Discontinuation of Study Treatment

Use of the following therapies during the study until completion of study treatment will require permanent discontinuation of study treatment and withdrawal from the study except when specified otherwise below:

- High- to ultra-high potency TCS (Class III-I) administered for ≥7 consecutive days. TCS Classes III-I are based on WHO classification of topical corticosteroids^{34,35}. See CRF guidelines.
- Systemic corticosteroids (intranasal sprays, corticosteroid inhalers, ophthalmic and ear drop corticosteroids are allowed) (requires permanent discontinuation of study treatment but participants are not required to withdraw from the study).
- S1P receptor modulators (eg, fingolimod, ozanimod).
- α4β1 integrin receptor antagonist (eg. natalizumab).
- Anti-CD20 antibodies (eg, rituximab, ocrelizumab), anti-CD52 antibodies (eg, alemtuzumab), other cell depleting therapies (eg, bone marrow transplantation, total body irradiation).

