- Systemic immunosuppressive/immunomodulating drugs (eg, cyclosporine, azathioprine, methotrexate), including topical or oral JAK inhibitors (requires permanent discontinuation of study treatment but participants are not required to withdraw from the study).
- Any biologic treatment, anti-IL4/13 antibodies (eg, dupilumab), anti-IL13 antibodies (eg, tralokinumab, lebrikizumab), anti-IL17A antibodies (eg, secukinumab), anti-IL12/23 antibodies (eg, ustekinumab), anti-IL31 antibodies (eg, nemolizumab), anti-IL23 antibodies (eg, risankizumab) requires permanent discontinuation of study treatment, but participants are not required to withdraw from the study.
- Any IV medications taken in response to serious infection that required hospitalization or treatment.

- Moderate/strong inhibitors or inducers that inhibit or induce at least 2 of the following: cytochrome P450 (CYP)2C8, CYP2C9, and CYP3A4 (e.g., fluconazole, rifampin, enzalutamide, Section 10.8.1).
- Live-attenuated replication-competent vaccines starting 6 weeks prior to baseline (Day 1), during study treatment and for 4 weeks after the last dose of study treatment.
- Start, stop, or change in dosage of any anti-arrhythmic drugs (Class I to IV) within 1 week before or after treatment initiation or reinitiation following dose interruption of a duration requiring in-clinic cardiac monitoring (Section 6.1.1).
- Any investigational drug other than the study treatment.

Participants who complete the treatment period no longer need to abstain from the medications that were prohibited during the treatment periods, unless noted otherwise (eg, live attenuated vaccines for 4 weeks after the last dose of study treatment).

For prohibited concomitant procedures:

- Participants may not undergo phototherapy for AD or artificial tanning (beds, booths, or lamps), including psoralen and ultraviolet A, ultraviolet B, tanning booth, and excimer laser.
- Participants should not take bleach baths.
- Participants should not undergo cell depleting therapies (eg, bone marrow transplantation, total body irradiation).
- Participants should not undergo major elective surgery while on study treatment.
- Participants may not donate blood during the study and for 30 days after the last dose of study treatment.
- Participants may not donate sperm, or oocytes during the study and for 28 days after the last dose of study treatment.

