6.9.4. Rescue Medicine

Medicated and non-medicated rescue medications are not permitted during the Part 1 DB portion. For Part 1 OLE and Part 2 medicated and non-medicated topical treatments for AD will be permitted at the discretion of the investigator and in accordance with their usual practice.

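### Protocol 6.9.3 prohibits medicated AD topicals, and ends participation for a week or more of potent TCS, in the open-label phases where four other sections allow them

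*Protocol*

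**What the plan says.** Protocol 6.9.3 contains two lists.

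- The first requires the participant to stop the medication but not study treatment. It opens: "The following therapies are prohibited during the study until completion of study treatment". It covers lower-potency TCS, calcineurin inhibitors, crisaborole, Class III-I TCS used for fewer than 7 consecutive days, and a further bullet of other topicals such as tars and antibiotic creams.
- The second carries a heavier consequence. Use of a listed therapy "during the study until completion of study treatment will require permanent discontinuation of study treatment and withdrawal from the study", unless a bullet says otherwise. One bullet is "High- to ultra-high potency TCS (Class III-I) administered for ≥7 consecutive days", and it states no exception. A later bullet covers systemic immunosuppressive drugs, "including topical or oral JAK inhibitors (requires permanent discontinuation of study treatment but participants are not required to withdraw from the study").

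The section then says when the restrictions lift: "Participants who complete the treatment period no longer need to abstain from the medications that were prohibited during the treatment periods".

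Protocol 6.9.4, the next section, bars rescue medication only in the Part 1 DB period and continues: "For Part 1 OLE and Part 2 medicated and non-medicated topical treatments for AD will be permitted at the discretion of the investigator". The synopsis, Protocol 4.1 and SAP 2.3 repeat that permission. Those three also tie the TCS restriction to the DB phase. In the synopsis, TCS and other medicated AD topicals "must be discontinued at least 1 week prior to baseline (Day 1) and are not permitted in the double-blind treatment period".

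SAP Appendix 4 treats initiation of a prohibited medication as an intercurrent event in the Part 1 DB phase only.

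**The concern.** A participant on open-label etrasimod who has a flare and uses a potent topical steroid for a week is within the rules under 6.9.4. Under 6.9.3 the same participant must stop study treatment for good and leave the study. Neither section refers to the other, and no order of precedence is stated.

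Long-term safety is the primary objective of the OLE and Part 2 (Protocol Section 3). A rule that wrongly stops dosing there removes the exposure those phases exist to collect. It could also make deviation reporting inconsistent. SAP 6.5.6 summarizes important protocol deviations for the OLE and Part 2, and two sites could code identical topical use differently.

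**Working it through.** The plan gives no figure to reproduce on this point, so the check is mainly a comparison of text, followed by simple arithmetic on scope.

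**Do the OLE and Part 2 fall inside the 6.9.3 ban?** Yes. The ban runs to the end of study treatment. Protocol Section 6 defines study intervention as both etrasimod and placebo, so open-label dosing counts.

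**Does the release sentence end the ban at Week 16?** No. It applies once the treatment period is complete, and the schedules of activities label both open-label phases as treatment periods. For Part 1, for example: "Home health and/or telehealth visits may apply for certain extenuating circumstances only during the OLE Treatment period".

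**Does the allowance for exceptions in the second list rescue the TCS bullet?** No. On its natural reading it points to the bullets that waive study withdrawal: systemic corticosteroids, immunosuppressants including JAK inhibitors, and biologics. The TCS bullet has no such waiver. A more generous reading would still leave the first list's ban in force.

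**Side by side:**

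| Source | Medicated AD topicals in DB | In OLE and Part 2 |
|---|---|---|
| Protocol 6.9.3 | Prohibited | Prohibited; Class III-I TCS for 7 or more days means discontinuation and withdrawal |
| Protocol synopsis | Prohibited | Allowed at investigator's discretion |
| Protocol 4.1 | Prohibited | Allowed at investigator's discretion |
| Protocol 6.9.4 | Barred as rescue medication | Allowed at investigator's discretion |
| SAP 2.3 | Prohibited | Allowed at investigator's discretion |

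Four statements agree and 6.9.3 is the outlier. SAP Appendix 4 fits the majority. The sanction is also out of proportion: a week of potent TCS triggers withdrawal from the study, whereas systemic corticosteroids require only stopping study treatment.

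**Scope:**

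- Part 1 planned treatment = 16 DB weeks + 52 OLE weeks = 68 weeks. Share under conflicting rules = 52/68 = 0.765, about 76%.
- Part 2: 52/52 = 100%.
- Most exposure one participant could lose, if a 7-day course starts with the first open-label dose: 52 − 1 = 51 weeks. The least is close to zero, for a course near the end of treatment.

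No count of affected participants is possible, because neither document gives a rate of Class III-I TCS use.

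**The case against.** The strongest reply is that the intended rule is plain. Four statements agree, and 6.9.4 is specific to phase and directly follows 6.9.3, so an ordinary reader would let it govern. That is very probably the intent. But the TCS bullet in 6.9.3 is specific too, giving potency class, duration and consequence, and Protocol 8.1 rules out waivers. A site has no written ground for ignoring it.

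Safeguards can be cited. Protocol 10.8.1 leaves continued participation after prohibited-medication use to the investigator's judgment, after consulting the sponsor. Its wording is broad, but it sits in the drug-interaction appendix and may not be read as reaching topical steroids. Protocol 7.1 separates stopping treatment from leaving the study and keeps participants for safety evaluation. That does not restore exposure: follow-up after the last dose is only about 4 weeks (Protocol 1.3.2 and 8.4.1).

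Both TCS bullets refer to CRF guidelines that are not among the documents. Those guidelines might handle TCS by phase, which limits what can be said about practice at sites but does not change the protocol's wording.

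The scope figures are not rates of harm. That stands. Some participants who need prolonged potent TCS might also stop under the EASI-50 rule in Protocol 7.1.5, at Week 32 of Part 1 or Week 16 of Part 2, so the exposure actually lost could be less than the maximum.

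On topical JAK inhibitors, the express prohibition can reasonably be read as prevailing over the general permission. That part is a request for clarification only.

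**Conclusion.** The conflict is real and lies in the current text. Section 6.9.3 is an operative rule that is wrong as written for the OLE and Part 2: followed literally, it would end study treatment for a use that four other statements allow. It should be corrected.

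The consequence is bounded. It depends on sites following 6.9.3 over 6.9.4, and its frequency is unknown. The loss that matters is open-label exposure, up to 51 weeks for one participant. The Part 1 DB efficacy analyses are unaffected, because the prohibited-medication intercurrent event applies only there and 6.9.3 agrees with the other sections for that period. Part 2 takes place only if the interim analysis supports it. Confidence is high on the conflict in wording; nothing firm can be said about how often it would change a participant's course.

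**What to change.** In Protocol 6.9.3, add a phase qualifier limiting three bullets to the Part 1 DB period:

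- first list: the bullet on lower-potency TCS, calcineurin inhibitors, crisaborole and short courses of Class III-I TCS;
- first list: the bullet on other medicated topicals, as far as they are used for AD;
- second list: the bullet on Class III-I TCS for 7 or more consecutive days.

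Add one sentence stating whether topical JAK inhibitors remain prohibited in the OLE and Part 2. The sponsor may well want to keep that ban because of additive immune effects; the text only needs to say so.

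The cost is a wording change in one section, with no new data and no new analysis. The same edit could settle whether the bar on new additive-containing emollients also holds in the open-label phases, since 6.9.4 allows non-medicated topicals there.

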7. DISCONTINUATION OF STUDY INTERVENTION AND PARTICIPANT DISCONTINUATION/WITHDRAWAL

7.1. Discontinuation of Study Intervention

It may be necessary for a participant to permanently discontinue study intervention. Reasons for permanent discontinuation of study intervention include the following:

- Adverse events noted below (participants with AEs listed below, irrespective of
 causality, will be discontinued from the study intervention) NOTE: Sub bullets below
 are examples and are not intended to be an all-inclusive list.
 - Second episode of confirmed Grade 4 lymphopenia in the same participant (Protocol Sections 10.10.1, 10.10.2)
 - Repeated episode of a serious infection for the same participant (Protocol Section 10.10.2)
 - o Diagnosis of PML (Protocol Section 10.11)
 - Diagnosis of PRES (Protocol Section 8.4.8)
 - ECG changes (Protocol Section 7.1.3)
 - Suspected intolerance associated with first dose cardiac effects (Protocol Section 10.10.3.2)
 - o Malignancy (Protocol Section 8.4.8)
 - o HBV DNA above LLQ (Protocol Section 8.3.7)
 - O Active, latent, or inadequately treated TB infection (Protocol Section 8.3.5)

 PFIZER CONFIDENTIAL

 CT02 GSOP Clinical Protocol Template Phase 1.2.3.4 (01.4 pril 2022)

- o Clinically significant respiratory AE and or a decline in confirmed PFT values (FEV1 and/or FVC below 50% of the predicted values; Protocol Section 10.10.4)
- o Confirmed macular edema (Protocol Section 10.10.5)
- Drug-induced liver injury confirmed cases after all results of reasonable investigations have been received as per Protocol Section 10.5, and alternative etiology have been excluded (Protocol Section 10.10.5)
- Clinically significant safety concern as per investigator's judgement at Week 16 (Protocol Section 7.1.1)
- Death
- Lost to follow up
- Physician decision
- Pregnancy
- Protocol deviation
- Study terminated by Sponsor
- Withdrawal by participant
- Lack of Efficacy

Discontinuation of study intervention does not represent withdrawal from the study. If study intervention is permanently discontinued, the participant should remain in the study to be evaluated for safety. See the SoA for data to be collected at the time of discontinuation of study intervention and follow-up for any further evaluations that need to be completed.

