7.1.5. Lack of Efficacy

Lack of efficacy will result in permanent discontinuation of study intervention only for the reason below:

 Participants who do not meet EASI-50 criteria at Week 32 in Part 1 (Week 16 of OLE) or at Week 16 of Part 2. In the case of lack of efficacy, the participant will be permanently withdrawn from administration of study intervention, complete Early Termination procedures, and then complete the 2- week (SFU 1) and 4-week (SFU 2) follow-up visits.

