10.8. Appendix 8: Prohibited Concomitant Medications That May Result in DDI 10.8.1. Prohibited Concomitant Medications That May Result in DDI

Moderate or strong inhibitors or inducers that inhibit or induce at least 2 of the following are prohibited: Cytochrome P450 (CYP)2C8, CYP2C9, and CYP3A4. Examples include fluconazole, rifampin, and enzalutamide.

The Pfizer study team is to be notified of any prohibited medications taken during the study. After consulting with the sponsor, the investigator will make a judgment on the ongoing participation of any participant with prohibited medication use during the study.

This list of drugs prohibited for potential DDI concerns with the IMP may be revised during the course of the study with written notification from sponsor, to include or exclude specific drugs or drug categories for various reasons (eg, emerging DDI results for the IMP, availability of new information in literature on the DDI potential of other drugs).

Investigators should consult the product label for any other medication used during the study for information regarding medication that is prohibited for concomitant use.

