10.10.2. Serious Infections Monitoring

Low lymphocyte counts observed with the use of other S1P receptor modulators in patients with multiple sclerosis have been associated with serious and atypical infections. ^{4,5,46} Investigators should remain vigilant in monitoring for signs and symptoms of serious and atypical infections during the study and after discontinuation of study treatment. Serious infection monitoring (refer to definition for Serious Adverse Events in Section 10.3.2) requires a temporary interruption of study intervention. Study intervention cannot be restarted until the serious infection has resolved per investigator judgement (investigator may discuss restarting study intervention with the medical monitor, if needed). If the participant cannot be restarted on study intervention, then the participant must be permanently discontinued.

Participants will be queried for signs and symptoms of PML. If a participant exhibits signs and symptoms suspicious for PML, study treatment must be interrupted and cannot be restarted until diagnostic evaluation is completed and PML has been excluded. The study medical monitor should be informed of any suspected cases of PML. Refer to Section 10.11 for signs and symptoms of PML and a PML case evaluation algorithm. In the evaluation and management of treatment emergent infections, the Investigator may consult with infectious disease or relevant experts, as needed.

All radiologic images (eg, magnetic resonance imaging, computer tomography, X rays) and diagnostic laboratory test results performed by local laboratories/facilities should be retained as source documents by study sites and made available upon request by the Sponsor for central adjudication as needed. All infections that develop during the study will be reported as AEs on the AE eCRF page.

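### Protocol 6.9.3 conflicts with 10.10.2, 6.9.4 and 10.8.1 on IV treatment of serious infection, topical AD therapy and CYP inhibitors or inducers

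*Protocol*

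**What the plan says.** Section 6.9.3 has two lists. Therapies on the first must be stopped while study drug continues. They include lower-potency topical corticosteroids (TCS), calcineurin inhibitors and crisaborole. Use of a therapy on the second list "will require permanent discontinuation of study treatment and withdrawal from the study except when specified otherwise below". Both lists run until study treatment is completed, with no distinction between the double-blind (DB) period, the OLE and Part 2.

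Three entries on the second list carry a written exemption from study withdrawal: systemic corticosteroids, systemic immunosuppressants including JAK inhibitors, and biologics. The others carry none. Among them are Class III-I TCS for 7 or more consecutive days, "Any IV medications taken in response to serious infection that required hospitalization or treatment", and moderate or strong CYP inhibitors or inducers. The CYP entry refers the reader to 10.8.1.

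Other sections say:

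- **7.1:** "If study intervention is permanently discontinued, the participant should remain in the study to be evaluated for safety". Its examples of adverse events that end treatment include a repeated serious infection.
- **10.10.2:** a serious infection "requires a temporary interruption of study intervention", and "Study intervention cannot be restarted until the serious infection has resolved per investigator judgement".
- **6.9.4:** in the Part 1 OLE and Part 2, "medicated and non-medicated topical treatments for AD will be permitted at the discretion of the investigator". The synopsis, Protocol 4.1 and SAP 2.3 repeat this.
- **10.8.1:** after consulting the sponsor, "the investigator will make a judgment on the ongoing participation of any participant with prohibited medication use".
- **7.1.5:** participants stopped for lack of efficacy "complete Early Termination procedures, and then complete the 2- week (SFU 1) and 4-week (SFU 2) follow-up visits". Section 6.9.3 has no matching sentence.

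**The concern.** An investigator with one of these events in front of them gets two instructions with different results for the participant. One section says stop for good and leave the study. Another says pause and perhaps restart, or carry on, or decide case by case.

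The main stake is long-term safety follow-up. Part 2 exists to supply about 340 participants treated for 52 weeks, and long-term safety is a primary objective of both the OLE and Part 2. Infections are an adverse event of special interest. Under 6.9.3, a participant given IV medication for a first serious infection leaves, so nothing is learned about treatment after recovery. A participant given a potent topical steroid in the OLE or Part 2 leaves because of treatment that another section allows. Sites that resolve the conflict differently would also make discontinuation counts hard to interpret.

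**Working it through.** The plan states no figure on this point. The check is a count and a comparison of sections.

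**1. Reach of the withdrawal default.** The entries on the second list of 6.9.3 are: (1) potent TCS, (2) systemic corticosteroids, (3) S1P modulators, (4) integrin antagonists, (5) anti-CD20, anti-CD52 and cell-depleting therapy, (6) immunosuppressants and JAK inhibitors, (7) biologics, (8) IV medication for serious infection, (9) CYP inhibitors or inducers, (10) live vaccines, (11) anti-arrhythmic changes, (12) other investigational drugs. Entries 2, 6 and 7 are exempt from study withdrawal: 12 − 3 = 9 entries under the default.

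**2. The three direct conflicts.**

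| Event | 6.9.3 | Other section |
|---|---|---|
| IV medication, first serious infection | Permanent stop and withdrawal | 10.10.2: interrupt; restart possible after resolution |
| Class III-I TCS for ≥7 days, OLE or Part 2 | Permanent stop and withdrawal | 6.9.4: medicated topicals allowed |
| Lower-potency TCS, calcineurin inhibitor or crisaborole, OLE or Part 2 | Stop the topical, keep study drug | 6.9.4: medicated topicals allowed |
| CYP inhibitor or inducer | Permanent stop and withdrawal | 10.8.1, cited by the entry: investigator judgement after consulting the sponsor |

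- *Serious infection.* If 6.9.3 is followed, the repeated-episode rule in 7.1 can be reached only by participants whose first serious infection was managed without IV medication. The conflict is confined to those who received it.
- *Topicals.* One could try to read 6.9.4 as allowing only what 6.9.3 does not prohibit. But 6.9.3 names topical steroids of every class, calcineurin inhibitors and crisaborole, and its immunosuppressant entry adds topical JAK inhibitors. That would leave the permission in 6.9.4 with little content. Only the second-list entries cost a participant study drug; the first-list clash concerns whether the topical may be used.
- *CYP entry.* The mandatory rule and the judgement rule are reached from the same line.

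**3. The default against 7.1.** Section 7.1 separates stopping drug from leaving the study and keeps the participant for safety evaluation. Section 6.9.3 joins the two for 9 entries. Neither section mentions the other.

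**4. Follow-up visits.** SFU 1 and SFU 2 together hold 2 hematology samples, 2 PML queries and 1 TBNK panel (SFU 2 only). Section 7.2 says a withdrawn participant leaves the study at that point, but it also refers to the SoA for follow-up. The SoA and Section 4.1 tie both visits to the last dose.

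**5. Estimands.** Under E1, starting a prohibited medication or stopping treatment before Week 16 already makes the participant a non-responder. Under E2, data after either event are already set to missing and imputed. Study withdrawal adds nothing to either. The supportive estimands E1a and E2a use post-event data, so they could lose a rating if a withdrawn participant's later visits were not done.

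**The case against.** The best defence is that 6.9.3 is a specific rule and 7.1 a general one. Section 7.1 says only that participants should remain. Section 6.9.3 announces exceptions and writes out three, which looks deliberate, and 7.2 lists protocol deviation as a reason for leaving the study. This has force: the tension with 7.1 alone would not carry the point. It does not resolve the three direct conflicts, where both rules address the same event.

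On infections, 10.10.2 sets a condition for restarting and does not promise it. It adds that a participant who cannot restart must stop permanently. The examples in 7.1 are expressly not exhaustive, and stopping an immunomodulator is the cautious error. So 6.9.3 may have been meant as a stricter rule for infections needing IV medication. If so, 10.10.2 should say it, since as written it governs all serious infections.

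A reader might go further in three ways that the documents do not support:

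- **Safety visits and AE data would be lost for nine kinds of therapy.** The SoA, 4.1 and 4.2 call for the 2- and 4-week visits after the last dose. Section 8.4.1 continues AE collection for at least 4 weeks after the last dose unless consent is also withdrawn. Sections 8.3.6 and 8.4.3 require follow-up of significant abnormal laboratory values and ongoing events. Missed visits are a secondary risk from ambiguous wording.
- **10.8.1 contradicts all nine entries.** Its sentence is broad, but it sits in an appendix on drug interactions and only the CYP entry cites it.
- **9 of 12 measures exposure to the problem.** It counts bullets. Natalizumab and the anti-CD20 and anti-CD52 antibodies also fall within the exempt entry for any biologic, and the exempt entries cover most of the systemic AD drugs named in inclusion criterion 4.

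**Conclusion.** The point stands as a set of conflicting operative rules in current text: IV medication for a serious infection, topical AD therapy in the OLE and Part 2, and the CYP entry. The first two matter most, because following 6.9.3 would end treatment and follow-up in participants whom 10.10.2 could restart or whose treatment 6.9.4 permits. The withdrawal default is a lesser, related inconsistency with 7.1.

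The topical conflict could arise in about 340 Part 2 participants and in those of the roughly 60 in Part 1 who enter the OLE. How many would be affected cannot be sized, because the documents give no rate for serious infection, IV medication, potent-TCS use or CYP-drug use. E1 and E2 are unaffected, so nothing here bears on the primary or secondary efficacy estimates. The conclusion assumes that sites apply each section as written and have no separate guidance settling the order of precedence.

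**What to change.** Amend 6.9.3 in four places:

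1. Make the IV-medication entry defer to 10.10.2 for a first serious infection, leaving the repeated-episode rule in 7.1 to govern a second.
2. Limit the topical AD entries in both lists to the Part 1 DB period, and state whether topical JAK inhibitors follow the same rule.
3. Make the CYP entry defer to 10.8.1.
4. Replace the study-withdrawal clause with a sentence modelled on 7.1.5: participants who stop drug because of prohibited therapy complete ET, SFU 1 and SFU 2 unless consent is withdrawn.

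Keep the IV and CYP entries on the prohibited list during the DB period, so that identification of the intercurrent event under SAP Appendix 4 does not change. The cost is protocol wording only. The visits are already in the SoA, no analysis changes, and 7.1.5 supplies the model sentence.
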